10.1.4 SAEs

An SAE is defined as any untoward medical occurrence that at any dose:

- 1. Results in DEATH.
- 2. Is LIFE THREATENING.
 - The term "life threatening" refers to an event in which the subject was at risk of death at the time of the event; it does not refer to an event that hypothetically might have caused death if it were more severe.
- 3. Requires inpatient HOSPITALIZATION or prolongation of existing hospitalization.
- 4. Results in persistent or significant DISABILITY/INCAPACITY.
- 5. Is a CONGENITAL ANOMALY/BIRTH DEFECT.
- 6. Is an IMPORTANT MEDICAL EVENT that satisfies any of the following:
 - May require intervention to prevent items 1 through 5 above.
 - May expose the subject to danger, even though the event is not immediately life threatening or fatal or does not result in hospitalization.
 - Includes any event or synonym described in the Takeda Medically Significant AE List (Table 10.a).

Table 10.a Takeda Medically Significant AE List

Term			
Acute respiratory failure/acute respiratory distress syndrome	Hepatic necrosis		
Torsade de pointes / ventricular fibrillation / ventricular	Acute liver failure		
tachycardia	Anaphylactic shock		
Malignant hypertension	Acute renal failure		
Convulsive seizure	Pulmonary hypertension		
Agranulocytosis	Pulmonary fibrosis		
Aplastic anemia	Confirmed or suspected endotoxin shock		
Toxic epidermal necrolysis/Stevens-Johnson syndrome	Confirmed or suspected transmission of infectious agent by a medicinal product		
	Neuroleptic malignant syndrome / malignant hyperthermia		
	Spontaneous abortion / stillbirth and fetal death		

Note: Terms identified on the Medically Significant AE List represent the broad medical concepts to be considered as "Important Medical Events" satisfying SAE reporting requirements.

PTEs that fulfill 1 or more of the serious criteria above are also to be considered SAEs and should be reported and followed up in the same manner (see Sections 10.2.2 and 10.3).

10.1.5 AEs of Special Interest

AEs of special interest are to be reported and followed up in the same manner of other AEs (see Section 10.2.2).

An AE of Special Interest (serious or nonserious) is one of scientific and medical concern specific to the compound or program, for which ongoing monitoring and rapid communication by the investigator to Takeda may be appropriate. Such events may require further investigation in order to characterize and understand them. The reporting of specific AE of Special Interest are described in the following sections.

10.1.5.1 Skin and Allergic Type Reactions

Any subject who develops rash should undergo assessment to characterize the nature and location of the rash. Subjects should be adequately examined for any clinical features that might suggest a developing drug reaction with eosinophilia and systemic symptoms (DRESS), a developing toxic epidermal necrolysis (TEN) or Stevens-Johnson Syndrome (SJS). For example, all subjects who develop rash should undergo a physical examination and be monitored for the appearance of any of the following features (and findings should be recorded):

- a) Involvement of mucous membranes or conjunctiva.
- b) The development of skin pain.
- c) Urticaria, blistering, other skin lesions.
- d) Any evidence of angioedema.

CONFIDENTIAL

If there are subjects with symptoms of systemic reaction (eg, generalized rash), or signs of a severe rash (such as those outlined above) or if clinically appropriate then the following laboratory parameters should also be conducted and monitored accordingly: complete blood count with differentials, liver and renal functions tests, and urinalysis.

Any subjects showing symptoms or signs outlined above or if clinically indicated should also be assessed by a dermatologist and undergo an adequate diagnostic work-up (to assess for developing DRESS, TEN, or SJS).

Finally, consider taking photographs of rashes and, when appropriate, obtain skin biopsies.

For all cases of rash where an alternative causality is not known a skin or allergy type reaction eCRF form should be completed within 1 business day of the investigator's awareness of the event. If the alternative causality has been identified, then no skin or allergy type reaction eCRF should be completed.

10.1.5.2 Liver Injury

Management of liver toxicity AEs is described in Section 7.4 of the protocol. If ALT or AST >3×ULN, laboratory tests should be repeated within a maximum of 7 days, and preferably within 48 to 72 hours. If the ALT or AST remains elevated >3×ULN on these 2 consecutive occasions, and this observation cannot be explained by concomitant disease or another alternative causality, the abnormality should be recorded on an AE page. The investigator must contact the Medical Monitor for consideration of immediate discontinuation of study drug, discussion of the relevant subject details and possible alternative causalities.

If a subject is noted to have an ALT or AST >3×ULN and total bilirubin >2×ULN for which an alternative etiology has not been identified, the event should be recorded as an SAE and reported as per Section 10.3.1. In addition, an LFT increases eCRF must be completed and transmitted with the SAE

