Urine drug screen test kits will be supplied by the sponsor for UDS testing at the clinic. Urine for drug screening will not be sent to the central laboratory for testing. The central laboratory will perform laboratory tests for serum pregnancy, hematology and limited serum chemistries. Local UDS and urine pregnancy screening results must be confirmed prior to conducting the Baseline Visit. Serum pregnancy collected at Baseline should be sent to the central laboratory. In the case of a combined Screening and Baseline Visit the UDS and the urine pregnancy test will be done once

in the clinic and a serum pregnancy test will be sent to the central laboratory. The results of central laboratory tests will be returned to the investigator, who is responsible for reviewing and filing these results.

If subjects experience ALT or AST >3 ×ULN, follow-up laboratory tests (at a minimum, serum alkaline phosphatase, ALT, AST, total bilirubin, gamma-glutamyl transferase, and INR) should be performed within a maximum of 7 days and preferably within 48 to 72 hours after the abnormality

was noted. (Refer to Section 7.4 and Section 10.2.3 for the appropriate guidance on reporting abnormal liver function tests.)

If ALT or AST remains elevated >3×ULN on these 2 consecutive occasions, the investigator must contact the Medical Monitor for consideration of additional testing, close monitoring, possible discontinuation of sponsor-supplied drug. discussion of the relevant subject details and possible alternative etiologies. The abnormality should be recorded as an AE (please refer to Section 10.2.3).

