10.1.2 AEs

An AE is defined as any untoward medical occurrence in a clinical investigation subject administered a drug; it does not necessarily have to have a causal relationship with this treatment.

An AE can therefore be any unfavorable and unintended sign (eg, a clinically significant abnormal laboratory value), symptom, or disease temporally associated with the use of a drug whether or not it is considered related to the drug.

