10.2.3 Reporting of Abnormal LFTs

If a subject is noted to have ALT or AST elevated >3×ULN on 2 consecutive occasions, the abnormality should be recorded as an AE. In addition, an LFT Increases eCRF must be completed providing additional information on relevant recent history, risk factors, clinical signs and symptoms and results of any additional diagnostic tests performed.

If a subject is noted to have ALT or AST >3×ULN and total bilirubin >2×ULN for which an alternative etiology has not been identified, the event should be recorded as an SAE and reported as per Section 10.2.2. The investigator must contact the Medical Monitor for discussion of the relevant subject details and possible alternative etiologies, such as acute viral hepatitis A or B or other acute liver disease or medical history/concurrent medical conditions. Follow-up laboratory

tests as described in Section 9.1.8 must also be performed. In addition, an LFT Increases eCRF must be completed and transmitted with the Takeda SAE form (as per Section 10.2.2).

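### Protocol 10.1.5.2 ties the AE record of a confirmed ALT/AST >3×ULN to its being unexplained, while 9.1.8 and 10.2.3 record every confirmed case

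*Protocol*

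**What the plan says.** Three Protocol sections deal with a confirmed transaminase elevation.

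- **10.1.5.2 Liver Injury.** The trigger is "If the ALT or AST remains elevated >3×ULN on these 2 consecutive occasions". The text then adds: "and this observation cannot be explained by concomitant disease or another alternative causality, the abnormality should be recorded on an AE page". The LFT Increases eCRF appears here only in connection with the SAE.
- **10.2.3 Reporting of Abnormal LFTs.** Here the rule reads: "If a subject is noted to have ALT or AST elevated >3×ULN on 2 consecutive occasions, the abnormality should be recorded as an AE". No condition on cause is attached, and the LFT Increases eCRF is required for each such case.
- **9.1.8 Procedures for Clinical Laboratory Samples.** After the same two-test trigger: "The abnormality should be recorded as an AE (please refer to Section 10.2.3"). Again there is no condition on cause.

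For ALT or AST above 3×ULN with total bilirubin above 2×ULN and no alternative etiology, 10.1.5.2 says "the event should be recorded as an SAE and reported as per Section 10.3.1", whereas 10.2.3 says "the event should be recorded as an SAE and reported as per Section 10.2.2".

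The general AE definition in 10.1.2 states that "it does not necessarily have to have a causal relationship with this treatment".

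**The concern.** Liver injury is one of three AEs of special interest, alongside skin and allergic reactions and overdose. If sections with the same trigger give different recording rules, whether a confirmed elevation enters the AE data depends on which section the site consults and on an open-label investigator's opinion of its cause. The cases at risk are not a random subset: they are those judged to have another explanation. That judgment is meant to be recorded as an attribute of an AE, not used to decide whether there is an AE to record.

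The second issue is the citation for the serious case. Section 10.3.1 describes the sponsor's reporting to authorities, investigators and ethics committees. It contains no step by which a site reports an SAE to the sponsor.

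**Working it through.** The plan states no figure on this point, so the check compares the current text. The amendment entries in Appendix E do not touch these sections.

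**1. The three sections side by side**

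| | 9.1.8 | 10.1.5.2 | 10.2.3 |
|---|---|---|---|
| Trigger | >3×ULN, two consecutive tests | same | same |
| AE record called for | every confirmed case | unexplained cases | every confirmed case |
| LFT Increases eCRF | not mentioned; refers to 10.2.3 | SAE case only | every confirmed case |
| With bilirubin >2×ULN, no alternative etiology | not mentioned | SAE, cites 10.3.1 | SAE, cites 10.2.2 |

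**2. A test case (assumed).** A subject has ALT at 4×ULN on two consecutive tests, and the investigator attributes it to a concomitant medicine. Under 9.1.8 the site records an AE. Under 10.2.3 it records an AE and completes the LFT Increases eCRF. Under 10.1.5.2 neither is called for.

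**3. Against the Protocol's general AE rules.** Section 10.1.2 defines an AE without regard to cause. Section 10.2.1.2 requires all AEs to be documented whatever the investigator concludes about drug relationship. Section 10.1.7 classes as not related the events that other factors, including underlying disease and concomitant medication, can reasonably explain. That is essentially the group left outside the 10.1.5.2 recording condition.

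**4. Whether another section settles it.** Section 10.2.1.3 requires AEs of special interest to be recorded as AEs, but identifies them by the criteria in 10.1.5, which leads back to the narrower rule. Section 10.1.3 asks for the diagnosis to be recorded when it is known. That does not dispose of an elevation attributed to a medicine with no separate diagnosis.

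**5. How a case reaches the tables.** SAP 7.9 covers adverse events, vital signs and weight, and the C-SSRS. It has no summary of liver laboratory values. A confirmed elevation therefore reaches the planned safety tables through the AE record. SAP 7.9.1 summarizes TEAEs regardless of relationship in its high-level tables, but it can only summarize what sites record.

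**6. The cross-reference.** Section 10.2.2 is the site procedure, with the SAE form completed and transmitted within 24 hours. Section 10.3.1 sets the sponsor's 7- and 15-day limits to authorities; the site's only task there is to forward expedited reports to its IRB or IEC. Both 10.1.5.2 and 10.2.3 limit the SAE to cases without an identified alternative etiology, so on this event they differ only in the section cited.

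**7. Size.** Appendix A schedules serum chemistry at Baseline and Week 12 only, so few confirmed cases are likely. As an assumed illustration, take 2 confirmed cases among 120 treated subjects:

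- All recorded: 2/120 = 1.7%.
- One judged explained and not recorded: 1/120 = 0.8%.
- Both judged explained and not recorded: 0/120 = 0%.

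These counts show the mechanism. They are not an estimate.

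**The case against.** The strongest reply is that 10.1.5.2 does not forbid a record. A reader might infer that a site following it records nothing for an explained elevation, but the section only says when a record is called for. The neighbouring 10.1.5.1 shows how the Protocol words an actual exclusion: it says outright that the special form is not completed once another cause of a rash is identified. Section 10.1.5.2 has no such sentence. It could be read as defining the special-interest subset, with 10.2.3 as the general rule, and 9.1.8 points to 7.4 and 10.2.3 for reporting. A site that applies all three sections together would record the test case. This stands in part: the loss is possible, not certain. The Protocol nowhere says which section governs, however, and 10.1.5 presents its subsections as the place where reporting of these events is described.

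A reader might also infer that citing 10.3.1 delays the most serious liver report, or that 9.1.8 and 10.2.3 both name the 24-hour procedure. The documents support neither. Only 10.2.3 cites 10.2.2 for this event; 9.1.8 does not mention the serious case. The site already has a 24-hour route: 10.2.2 applies to any SAE in the AE collection period, 10.1.5 cites 10.2.2, 10.2.1.3 sets a 24-hour report for clinically significant events of special interest, and Appendix B item 12 requires notice of an SAE within 24 hours. This objection stands, and the citation is a wrong section number with little risk of delay.

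Third, 10.1.3 says that pre-existing conditions are not recorded as AEs unless they worsen or complicate. An elevation fully accounted for by a stable concurrent disease is properly left out, so the reference to concomitant disease in 10.1.5.2 is partly consistent with the general rules. This stands and limits the fix.

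Finally, the study is single-arm and Protocol 13.1.4 plans no inferential safety statistics, so there is no between-arm bias. That is correct; what remains is completeness of the descriptive count.

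**Conclusion.** The inconsistency in AE recording is real and in the current text. For a confirmed ALT/AST >3×ULN with an alternative explanation, 9.1.8 and 10.2.3 call for an AE record and 10.1.5.2 does not; the LFT Increases eCRF requirement differs in the same way between 10.2.3 and 10.1.5.2. Because the SAP has no liver laboratory summary, an explained case may be absent from the safety tables. Any shortfall would run in one direction, toward a lower count, but only to the extent that sites follow 10.1.5.2 over the other two sections. The documents do not show how many cases that would be.

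The routing of the serious case is a secondary editorial error. Neither issue touches the primary endpoint. The point merits correction because it affects captured safety data on an event of special interest and is cheap to put right.

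**What to change.** Reconcile 10.1.5.2 with 9.1.8 and 10.2.3:

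- Remove the unexplained-only condition from AE recording, so that a confirmed ALT/AST >3×ULN is recorded whatever its presumed cause, subject to 10.1.3: record the diagnosis where one is known, and do not record a stable pre-existing condition unless it worsens.
- Capture the explanation in the causality field (10.1.7) and on the LFT Increases eCRF, and state in 10.1.5.2 that the form is required for every confirmed case, as in 10.2.3.
- Change the SAE cross-reference in 10.1.5.2 from 10.3.1 to 10.2.2.

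This takes short wording changes in the next amendment or a memo to sites. It concerns data capture and reporting only. The downside is a few more AE records judged not related.

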10.1.5.3 Overdose

Management of an overdose is described in Section 8.1.4 of this protocol. All cases of overdose (with or without associated AEs) will be documented as AEs. For events that meet the criteria of an overdose, an overdose eCRF form should be completed within 1 business day of the investigator's awareness of the event.

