6.0 STUDY DESIGN AND DESCRIPTION

6.1 Study Design

This study is an open-label, single-arm, multicenter, prospective, phase 4, interventional, flexible-dose study (as per the Trintellix US package insert) to determine the effectiveness of treatment with vortioxetine on subject goal achievement after a change in antidepressant medication for the treatment of MDD.

This study is comprised of a 3-week Screening Period (maximum 21 days), to be followed by a 12-week Treatment Period and a 4-week Safety Follow-up Period. Study visits will occur at Baseline (Day 1), and Weeks 2, 4 (Telephone), 6, 9 (Telephone), and 12. This study will enroll approximately 120 subjects and will be conducted at approximately 25 sites in the United States.

This study will enroll men and women between the ages of 18 and 65, inclusive, with a primary diagnosis of MDD, who have previously been treated within 6 weeks of Screening or are currently being treated for a major depressive episode (MDE) with an approved antidepressant for 6 weeks or longer at an adequate dose. Subjects who are dissatisfied with their current or recent antidepressant and are interested in a change in antidepressant treatment will be eligible for Screening.

The change in antidepressant medication will be based on the investigator's judgment in collaboration with the subject's level of dissatisfaction with their current or recent antidepressant treatment (ie, residual mood symptoms, intolerable side effects). Subjects also need to be eligible per the Trintellix United States (US) package insert and sign and date a written, informed consent form and any required privacy authorization prior to the initiation of any study procedures.

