8.1.4 Overdose

An overdose is defined as a known deliberate or accidental administration of study drug, to or by a study subject, at a dose above that which is assigned to that individual subject according to the treating physician per routine standard of care.

All cases of overdose (with or without associated AEs) will be documented on an Overdose page of the eCRF, in order to capture this important safety information consistently in the database. AEs associated with an overdose will be documented on AE eCRF(s) according to Section 10.0.

Serious adverse events (SAEs) associated with overdose should be reported according to the procedure outlined in Section 10.2.2.

In the event of deliberate or accidental drug overdose, general symptomatic and supportive measures should be used, along with immediate gastric lavage where appropriate. Intravenous fluids should be administered as needed. As in all cases of drug overdose, respiration, pulse, blood pressure, and other appropriate signs should be monitored and general supportive measures employed.

As with the management of all overdoses, the possibility of multiple drug ingestion should be considered. The physician may contact a poison control center for current information on the management of drug overdose.

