• Preplanned procedures (surgeries or therapies) that were scheduled prior to signing of informed consent are not considered PTEs or AEs. However, if a preplanned procedure is performed early (eg, as an emergency) due to a worsening of the pre-existing condition, the

worsening of the condition should be recorded as a PTE or an AE. Complications resulting from any planned surgery should be reported as AEs.

Elective surgeries or procedures:

• Elective procedures performed where there is no change in the subject's medical condition should not be recorded as PTEs or AEs, but should be documented in the subject's source documents. Complications resulting from an elective surgery should be reported as AEs.

Insufficient clinical response (lack of effectiveness):

• Insufficient clinical response, effectiveness, or pharmacologic action, should NOT be recorded as an AE. The investigator must make the distinction between exacerbation of pre-existing illness and lack of therapeutic effectiveness.

Overdose:

 Cases of overdose with any medication without manifested side effects are NOT considered PTEs or AEs, but instead will be documented on an Overdose page of the eCRF. Any manifested side effects will be considered PTEs or AEs and will be recorded on the AE page of the eCRF.

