10.2.1.3 AEs of Special Interest

If the subject experiences a skin rash or allergic type event as described above, liver injury, or overdose during the treatment period or the safety follow-up period based on the criteria outlined in Section 10.1.5 the event should be reported on a specific eCRF form within 1 business day of the investigator's awareness. Any relevant supporting documentation (ie, photographs, additional diagnostic testing, consultation reports) must be submitted to the sponsor. The special interest AEs have to be recorded as AEs in the eCRF.

If the AE of special interest/abnormality, which occurs during the treatment period or the follow-up period, is considered to be clinically significant based on the criteria below, it should be recorded in an AE Form or an SAE Form. The Form should be completed and reported to the clinical contract research organization (CRO)/Pharmacovigilance department within 24 hours.

Special interest AE/abnormality criteria include:

- Laboratory value threshold, if applicable.
- Premature termination for the AE of Special Interest, if applicable.
- Any other specific criteria.

AEs of special interest have to be recorded as AEs in the eCRF. An evaluation form along with all other required documentation must be submitted to the sponsor.

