7.9 Safety Analysis

7.9.1 Adverse Events

All adverse events will be coded using the latest version of MedDRA. In this dictionary, each verbatim term is coded to a lower level term, and then mapped to a preferred MedDRA term, which is then mapped to an SOC. All adverse events from the safety analysis set will be included in the data listings but only treatment-emergent adverse events will be included in the summary tables.

A treatment-emergent adverse event (TEAE) is defined as an adverse event with an onset that occurs after receiving study drug (AE start date \geq first dose date) and within 30 days after receiving the last dose of study drug (AE start date – last dose date \leq 30). Adverse events with onset occurring more than 30 days after last dose of study drug (AE start date – last dose date $>$ 30) will be listed, but not included in the summary tables. Adverse events with missing onset dates will be summarized regardless of severity and relationship to study medication.

Serious adverse events (SAEs) with onset that occurs after receiving study drug (AE start date \geq first dose date) and within 30 days after receiving the last dose of study drug (AE start date - last dose date \leq 30) will be summarized.

In the high-level adverse event summary tables, TEAEs will be summarized regardless of intensity and relationship to study drug. Within each subject, multiple reports of events that map to a common MedDRA term will be counted only once for calculating incidence rates.

At the adverse event level, the summary tables will present the number of subjects reporting each of these MedDRA events, ie, the numbers of subjects reporting 1 or more events that map to the given MedDRA term.

At the SOC level, the summary tables will present the number of subjects reporting 1 or more events that map to the given SOC. That is, the number of subjects reported at the SOC level will be less than or equal to the sum of the subject counts across all adverse events within that SOC.

In selected summaries (TEAEs overview, and TEAEs by SOC and preferred term), adverse events will be summarized by the number of events reported in addition to the number and percentage of subjects with at least one event.

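### Protocol 10.1.3 and 10.1.5.3 give opposite rules on whether a symptom-free study-drug overdose is an AE, and the SAP does not say how Overdose-page records are reported

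*Protocol*

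**What the plan says.** Four current protocol sections deal with recording an overdose.

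- **10.1.3**, on what counts as a pretreatment event (PTE) or AE: "Cases of overdose with any medication without manifested side effects are NOT considered PTEs or AEs". Such cases go on the Overdose page instead. Where there are symptoms, "Any manifested side effects will be considered PTEs or AEs and will be recorded on the AE page of the eCRF".
- **10.1.5.3**, overdose as an event of special interest: "All cases of overdose (with or without associated AEs) will be documented as AEs". It also asks for a dedicated form: "an overdose eCRF form should be completed within 1 business day of the investigator's awareness of the event".
- **10.2.1.3**, reporting of special-interest events, which names overdose among them: "The special interest AEs have to be recorded as AEs in the eCRF".
- **8.1.4**, which defines overdose as intake of study drug, deliberate or accidental, above the assigned dose: "All cases of overdose (with or without associated AEs) will be documented on an Overdose page of the eCRF". AEs associated with an overdose go on the AE form under Section 10.0.

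On the analysis side, SAP 7.9.1 lists all AEs from the safety analysis set, but "only treatment-emergent adverse events will be included in the summary tables". Overdose is not mentioned there or anywhere else in SAP 7.9.

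**The concern.** Under 10.1.3 a symptom-free overdose must not be recorded as an AE. Under 10.1.5.3 it must be. The AE tables and listings in SAP 7.9.1 are built from recorded AEs, so the same event could be present in them or absent from them according to which section the site consulted.

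Overdose is one of only three special-interest events that the protocol names, in a depression trial that assesses suicidality throughout treatment. A reader of the study report would expect a clear statement of how many overdoses occurred. As planned, no output gives that number in a way that does not depend on the recording rule followed.

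**Working it through.** The plan states no figure on this point, so there is none to reproduce. The check compares the texts and then adds a simple scale.

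**Step 1. Do the rules cover the same event?** 10.1.3 covers overdose with any medication. 10.1.5.3 refers to 8.1.4 for management, and 8.1.4 defines overdose for study drug. Study drug is a medication, so a study-drug overdose falls under both.

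**Step 2. Do they give different answers?**

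| Study-drug overdose | 10.1.3 | 10.1.5.3 with 10.2.1.3 | 8.1.4 |
|---|---|---|---|
| With symptoms | Symptoms recorded as AEs | Overdose recorded as an AE | Overdose page, plus AE form for associated AEs |
| Without symptoms | Not an AE; Overdose page | Recorded as an AE; overdose form as well | Overdose page; silent on AE status |

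The second row is the conflict: not an AE against an AE. 8.1.4 fits either answer, because it requires the Overdose page for every case and does not say that a symptom-free case may not also be an AE. 10.2.1.3 applies the criteria of 10.1.5, so it follows 10.1.5.3 and is not an independent rule. The contradiction is therefore essentially one sentence against one sentence.

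**Step 3. Is either text superseded?** No. Both stand in the body of the amended protocol, and Appendix E changes neither.

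**Step 4. What reaches the tables?** An overdose recorded as an AE with onset from the first dose to 30 days after the last dose meets the TEAE definition in SAP 7.9.1. One recorded only on the Overdose page is not in the AE data, and no other planned output in SAP 7.9 picks it up.

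**Step 5. Scale.** The only input is planned enrollment: "This study will enroll approximately 120 subjects" (Protocol 6.1). Assume that all of them are dosed and so form the safety analysis set. Let k be the number of subjects with a symptom-free overdose and no other TEAE.

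Difference in any-TEAE rate between the two rules = k / 120

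- k = 0: 0 points
- k = 1: 1/120 = 0.83 points
- k = 2: 2/120 = 1.67 points
- k = 3: 3/120 = 2.5 points

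The range 0 to 3 is an assumption, since the documents give no expected number. A subject who has another TEAE does not move the any-TEAE rate. Repeated events in one subject that map to the same coded term count once (SAP 7.9.1). The scale is therefore per subject, not per case.

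**The case against.** The strongest reply is that little is lost. Section 8.1.4 requires the Overdose page for every case, 10.1.3 sends symptom-free cases there, and 10.1.5.3 requires an overdose form. Taking that page and that form as the same record, the number of overdoses can be recovered whichever section a site follows. Only the additional AE label varies. This stands, and it limits the point.

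A site might also read 10.1.3 as the general rule and 10.1.5.3 as the specific one that overrides it for study drug. That is a reasonable guess, and it makes divergence between sites less certain. The protocol does not state such an order of precedence, however, and the wording of 10.1.3 includes study drug.

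A reader might infer more than the documents support in three respects.

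- *AE rates would not be comparable across the roughly 25 sites.* The SAP plans no AE summary by site, the study has one arm, and Protocol 13.1.4 rules out inferential statistics for safety. At most a pooled descriptive count is affected.
- *Special-interest counts would change.* The SAP plans no special-interest table or listing, so no planned count of that kind exists to change. The one-business-day form is triggered by the overdose itself, not by its AE status.
- *The AE tables will be wrong.* Nothing differs unless a symptom-free overdose occurs.

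**Conclusion.** The contradiction is real and stands in current text: for a symptom-free study-drug overdose, 10.1.3 cannot be reconciled with 10.1.5.3 and 10.2.1.3. If such an event occurs, its presence in the TEAE tables can depend on the section followed. The shift in the any-TEAE rate is about 0.8 percentage points per affected subject without another TEAE, and 0 to 2.5 points for an assumed 0 to 3 such subjects, taking about 120 dosed subjects as the denominator. The primary endpoint is untouched.

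A separate gap exists whichever rule is adopted: the SAP does not say how Overdose-page records will be reported. Overall this is an internal inconsistency of minor expected numerical effect. It deserves correction because the event is one the sponsor singled out and the correction is cheap.

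**What to change.** 1. **Protocol.** Reconcile 10.1.3, 10.1.5.3 and 10.2.1.3 to a single recording rule for an overdose without symptoms, and align 8.1.4 so that it states the same rule. This review takes no position on which of the existing rules is right.
2. **SAP 7.9.** Add a count of subjects with any overdose and a listing of all overdoses, both taken from the Overdose page and showing whether each was also recorded as an AE. That output gives the same number under either rule, and it also covers events already recorded inconsistently.

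The cost is a protocol clarification, one count and one listing. The protocol already requires the data, so no new collection is needed.
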